1. PURPOSE OF THE STUDY AND BACKGROUND

1.1. Hypothesis

- Chronic β -blocker or Angiotensin-Converting Enzyme (ACE)-inhibitor use is associated with decreased cumulative doses of vasopressors administered in the first 48 hours of septic shock

1.2. Purpose of the study

- The primary objective is to determine the effect of chronic β -blocker or ACE-inhibitor on cumulative vasopressor dosing in the first 48 hours of septic shock.
- The secondary objectives of this study
 - To determine the effect of chronic β -blocker or ACE-inhibitor on cumulative vasopressor dosing in the first 6, 12, and 24 hours of septic shock.
 - To determine the effects of chronic β -blocker or ACE-inhibitor on:
 - Adequate fluid resuscitation
 - Cumulative inotrope use (48 hours)
 - Cumulative hydrocortisone use at 6, 12, 24, and 48 hours
 - To determine cumulative vasopressor dose of patients on chronic calcium channel blocker or other antihypertensives (clonidine, hydralazine, angiotensin-receptor-blocker (ARB))

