4. SUBJECT IDENTIFICATION, RECRUITMENT AND CONSENT

4.1. Method Of Subject Identification And Recruitment

The study will be retrospective, and collected data will be a result of routine care. Adult patients 18 years of age or older with septic shock who received treatment with a vasopressor will be assessed for inclusion. Patients will be excluded if they are pregnant, transferred from outside hospital on vasopressor, admitted in cardiopulmonary arrest, prior arrest within 24 hours of admission to RUMC or if they required neuromuscular blockade.

Patients will be reviewed from 01/01/2012 to 08/1/2016. A list of MICU patients will be generated by the corresponding ICD-9 and ICD-10 codes for septic shock. Patients will be stratified into 4 groups: 1) not on either a chronic β -blocker or ACE-Inhibitor, 2) on chronic β -blocker, 3) on chronic ACE-Inhibitor, and 4) on both chronic β -blocker and ACE-inhibitor.

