5. METHODS AND STUDY PROCEDURES

5.1. Efficacy & Safety Assessments

The electronic medical record system (EPIC) will be used to collect data, including: patient age, gender, weight, height, BMI, race, past medical history (hypertension, diabetes, heart failure, afib/flutter, arrhythmia, history of myocardial infarction, history of CVA, CAD, CKD, dyslipidemia, asthma, COPD, cancer), Charlson Comorbidity Index, hospital length of stay, medical intensive care unit (MICU) length of stay. Prior to admission medications include: beta-blockers, ACE-inhibitors, amlodipine, diltiazem, ARBs, hydralazine, clonidine, hctz, loop diuretics, amiodarone, other antiarrhythmics. Vasopressor types and cumulative doses including: norepinephrine, epinephrine, phenylephrine, dopamine, and vasopressin. Epinephrine, phenylephrine, and dopamine will be converted to norepinephrine equivalents in concordance with other literature: 100 mcg dopamine equivalent to 1 mcg norepinephrine, 1 mcg epinephrine equivalent to 1 mcg norepinephrine, and 2.2 mcg phenylephrine equivalent to 1 mcg norepinephrine.^{5,6} Concomitant medications including: hydrocortisone, inotrope use, crystalloid type and amount, colloid use, albumin use, timing of antibiotics, and sedation choice if given. Clinical information collected include: Peak lactate, MAP, mechanical ventilation, in hospital mortality, 28 and 90 day mortality if available. SOFA score will be calculated as a measure of disease severity.

Study Timeline:

Date	Activity
September 2016	Rush University Medical Center IRB approval
October - November 2016	Data collection
December 2016	Data analysis
January 2017	Study presentation and manuscript preparation

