13.2. Planned Statistical Analysis

All data will be reported using descriptive statistics with mean (SD) used to describe normally distributed data and median (interquartile range [IQR]) used for non-normal data or data with a significant number of outliers. Distribution of data and assessment of normality will be analyzed. Chi-squared, Fisher's Exact and Student's t-test as appropriate will be used to assess differences among the study cohorts. A 4-way fixed effects ANOVA will be utilized for the primary outcome, cumulative vasopressor dose at 48 hours. *Post hoc* pairwise comparisons will be completed between groups using Bonferroni's, Turkey, or Hochberg's GT2 depending on final group size and variance. Statistical support for data evaluation will be sought out if necessary.

REFERENCES

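### The hydrocortisone outcomes are compared between cohorts without recording pre-admission systemic corticosteroid use, so an imbalance in it could bias them undetected

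*Combined protocol and SAP*

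**What the plan says.** Section 1.2 introduces a group of secondary outcomes with "To determine the effects of chronic β -blocker or ACE-inhibitor on" and includes in it "Cumulative hydrocortisone use at 6, 12, 24, and 48 hours". These are four time points of one cumulative measure.

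Section 5.1 defines the data to be abstracted. The home-medication sentence reads "Prior to admission medications include: beta-blockers, ACE-inhibitors, amlodipine, diltiazem, ARBs, hydralazine, clonidine, hctz, loop diuretics, amiodarone, other antiarrhythmics". All eleven entries are cardiovascular drugs or diuretics, and none is a corticosteroid. Hydrocortisone appears only as an in-hospital treatment: "Concomitant medications including: hydrocortisone, inotrope use, crystalloid type and amount". No field is described for its indication or for earlier steroid use. Asthma and COPD are recorded as past history ("dyslipidemia, asthma, COPD, cancer"), but no analysis is said to use them.

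Neither list of exclusions, in section 3.2 or section 4.1 ("Patients will be excluded if they are pregnant, transferred from outside hospital on vasopressor, admitted in cardiopulmonary arrest, prior arrest within 24 hours" and the items that follow), mentions prior steroid use or adrenal insufficiency.

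Section 13.2 plans "Chi-squared, Fisher's Exact and Student's t-test as appropriate will be used to assess differences among the study cohorts" and, separately, "A 4-way fixed effects ANOVA will be utilized for the primary outcome, cumulative vasopressor dose at 48 hours". It names no covariate, stratification, restriction or sensitivity analysis for any outcome.

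**The concern.** A patient who was taking a systemic corticosteroid before admission may be given hydrocortisone because of that history, whatever the vasopressor requirement. Such a patient adds to the cohort's hydrocortisone total for a reason unrelated to the β-blocker or ACE-inhibitor. If prior steroid users are unevenly spread over the four cohorts, the cohorts will differ in hydrocortisone even when the antihypertensives do nothing.

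There is one plausible route to uneven spread. Asthma and COPD can lead to steroid treatment and can also make a β-blocker less likely to be prescribed. That is clinical inference and not something the documents say. The gap does not depend on it, because imbalance from any cause would go unseen when the variable is not collected.

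At stake is the interpretation of four stated secondary outcomes. The plan would report a cohort difference as an effect of chronic therapy, and a reader could not judge how much of it came from prior steroid use.

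**Working it through.** **1. What each part of the plan does with prior steroid use**

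| Place | Could handle it by | Does it? |
|---|---|---|
| 3.2 and 4.1, eligibility | excluding prior users | No |
| 5.1, home medications | recording prior use | No: eleven entries, no corticosteroid |
| 5.1, concomitant medications | recording why hydrocortisone was given | No indication field |
| 5.1, past history | asthma and COPD as partial proxies | Collected, not used |
| 13.2, analysis | adjusting, stratifying or restricting | No |

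No step separates hydrocortisone given because of earlier steroid use from hydrocortisone given for the shock.

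**2. The plan's own figure is not touched**

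The sample size in section 13.1 concerns the primary outcome. For a one-way fixed-effects ANOVA with 4 groups, f = 0.25 and α = 0.05, the noncentrality is λ = N × f² = 180 × 0.0625 = 11.25. With 3 and 176 degrees of freedom the critical F is 2.6559 and the power is 0.8040. This matches the plan, and 180 is the smallest equal-group total reaching 0.80. At the planned 200 the power is 0.848. Nothing in this point changes these figures.

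**3. Illustration of size (all rates assumed, none in the documents)**

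Assumptions: no effect of the antihypertensives; hydrocortisone given to 90% of prior steroid users and 35% of others; prior use 5 to 15 percentage points more common in one cohort than in the other.

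Spurious difference in the proportion given hydrocortisone = imbalance × (0.90 − 0.35):
- 0.05 × 0.55 = 0.0275, or 2.8 points
- 0.15 × 0.55 = 0.0825, or 8.3 points

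Relative to the comparison cohort's rate, the result depends on how common prior use is there:
- No prior users: base 35%. 0.0275/0.35 = 8% and 0.0825/0.35 = 24%.
- 10% prior users: base 0.10 × 0.90 + 0.90 × 0.35 = 40.5%. 0.0275/0.405 = 7% and 0.0825/0.405 = 20%.

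Chance of p<0.05 in the direction of the imbalance, two-sided 5% test, normal approximation, 50 per cohort, base 35%: Φ[(d − 1.96 × SE₀)/SE₁], where SE₀ is the pooled and SE₁ the unpooled standard error.
- d = 0.0275 (37.75% v 35%): SE₀ = 0.0962, SE₁ = 0.0962. (0.0275 − 0.1886)/0.0962 = −1.67, giving 4.7%.
- d = 0.0825 (43.25% v 35%): SE₀ = 0.0976, SE₁ = 0.0973. (0.0825 − 0.1913)/0.0973 = −1.12, giving 13.2%.

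With no imbalance the figure is 2.5%. Pooling cohorts to 100 v 100 gives about 6% to 22%.

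Wider assumptions (imbalance 10 to 20 points; 80 to 100% of prior users treated v 30 to 50% of others) give 0.10 × (0.80 − 0.50) = 3 points up to 0.20 × (1.00 − 0.30) = 14 points. The chance of p<0.05 at 50 per cohort is then about 5% to 30%.

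**4. Limit of the illustration**

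The outcome in section 1.2 is cumulative use at four times. The calculation above is for the proportion ever treated. It shows that the mechanism can matter, but it does not estimate the bias in cumulative amount at any of the four times.

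**The case against.** The strongest case against the point has five parts.

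- **The mechanism is not in the documents.** A reader might infer that prior steroid users will concentrate in the two cohorts without a β-blocker. No text says that asthma or COPD discourages β-blockers, leads to chronic steroids, or determines hydrocortisone use in shock. Cancer is in the same history list and is another possible reason for steroids, with no evident link to β-blocker avoidance. This stands: a difference may arise, but its direction cannot be asserted.
- **The route covers only half of the exposure.** The airway-disease argument gives no reason for imbalance by ACE-inhibitor use, so it does not bear on ACE-inhibitor v neither, or both drugs v β-blocker alone. This stands for that route, although imbalance from other causes would be equally invisible.
- **Nobody has said hydrocortisone measures severity.** A reader might infer that lower hydrocortisone use will be read as milder shock. Section 2.2 does mention severity of shock as a matter of interest, but section 5.1 names the SOFA score as the severity measure. The documents do not support that stronger reading.
- **The loss may be repairable.** A reader might infer that nothing can be done once abstraction ends. The source is the existing electronic record, and asthma and COPD are available as partial proxies. On the other side, sections 10.2 and 11 put only de-identified data on the form and describe no link back to the chart, so returning for a missed variable may be difficult.
- **It is one case of a general gap.** Section 13.2 adjusts for nothing, including in the primary analysis. That is true and more important. Prior steroid use still deserves its own line, because it bears directly on receiving the drug that is the outcome and, unlike many other confounders, is not even collected.

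**Conclusion.** The point holds as a minor improvement. The documents establish that pre-admission systemic corticosteroid use is neither recorded, excluded nor analysed, while hydrocortisone is compared between cohorts as an effect of chronic β-blocker or ACE-inhibitor use. An imbalance could therefore bias these secondary outcomes without being seen.

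The conclusion rests on one clinical assumption, that prior steroid use makes hydrocortisone in shock more likely. The size and direction of any bias cannot be derived from the documents. The illustrative 3 to 8 points, with a 5% to 13% chance of a spurious significant result per pair of cohorts, depends wholly on assumed rates and concerns receipt, not cumulative dose. The primary outcome, its test and its sample size are not affected.

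**What to change.** 1. In section 5.1, add to the home-medication items: *systemic corticosteroid on the prior-to-admission medication list (yes/no)*. Report it by cohort with the other baseline data.
2. In section 13.2, keep all patients in the main comparison of cumulative hydrocortisone. Add one analysis at each of the four times that is either stratified by prior steroid use or excludes prior users, and say in advance which. Making the restricted group the main analysis would change the question and is not needed.
3. In section 1.2, word the hydrocortisone objective as an association with chronic β-blocker or ACE-inhibitor use.

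The cost is one more field, read from a list that is already being abstracted, and a somewhat smaller sample in an excluding analysis. If, for example, 10% of a cohort were prior users (assumed), that is 0.10 × 50 = 5 patients per cohort. A yes/no item does not separate short courses from long-term use, and it does not remove other confounding. Both limits should be stated with the results.

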1.3. Background

Literature suggests that extended periods of tachycardia, in patients with shock, are associated with increased mortality.¹⁻⁴ Interventional trials have suggested that increased doses of catecholamines are associated with the increased mortality and the administration of esmolol infusions may improve survival in patients with shock requiring vasopressor agents.¹

What remains unknown is the effect of home exposure to antihypertensive therapies, specifically beta-blockers and ACE-inhibitor. This study will evaluate the effects of home antihypertensive therapy with beta-blockers and ACE-inhibitor on vasopressor dose administered within the first 48 hours of septic shock.

2. STUDY DESIGN

2.1. Overview

This will be a retrospective four-cohort study. The four cohorts will be septic shock patients that were: 1) not on either a chronic β -blocker or ACE-Inhibitor, 2) on chronic β -blocker, 3) on chronic ACE-Inhibitor, and 4) on both chronic β -blocker and ACE-inhibitor

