13. DATA ANALYSIS AND MONITORING

13.1. Sample Size Determination

There are limited data for proper evaluation of a sample size. However, there was a smaller presented study that had a dramatic decrease in norepinephrine dose in patients on a β -blockers or ACE-inhibitors prior to admission for patients in circulatory shock of any kind.⁷ Using these data, estimated 48h cumulative mean dose for norepinephrine patients not on anti-hypertensives will be 50 mg (SD = 10) and estimated 48h cumulative mean dose for norepinephrine for beta blocker, ACE-Inhibitor, and beta-blocker + ACE-Inhibitor groups will be 25 mg (SD = 10). Using a 4-way fixed effects ANOVA power calculation with estimated effect size from previous study ($f = 1.08$) the total sample size would be 16

F tests – ANOVA: Fixed effects, omnibus, one-way

Analysis: A priori: Compute required sample size

Input: Effect size f	= 1.0825318
α err prob	= 0.05
Power (1- β err prob)	= 0.95
Number of groups	= 4
Output: Noncentrality parameter λ	= 23.4375020
Critical F	= 3.2388715
Numerator df	= 3
Denominator df	= 16
Total sample size	= 20
Actual power	= 0.9609969

However, the current proposed study is specifically looking at septic shock and the anticipated effect is unknown. Therefore, using a 4-way fixed effects ANOVA power calculation with a medium effect ($f = 0.25$) has a total sample size of 180 patients.

F tests – ANOVA: Fixed effects, omnibus, one-way

Analysis: A priori: Compute required sample size

Input: Effect size f	= 0.25
α err prob	= 0.05
Power (1- β err prob)	= 0.80
Number of groups	= 4
Output: Noncentrality parameter λ	= 11.2500000
Critical F	= 2.6559389
Numerator df	= 3

Denominator df	= 176
Total sample size	= 180
Actual power	= 0.8039869

A list of ICU patients will be generated by the corresponding ICD-9 and ICD-10 codes for septic shock during the inclusion time frame, randomized and screened until reaching the minimum power and equal groups (n = 200, 50 patients in each group)

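### Other home antihypertensives can sit in all four cohorts and the primary ANOVA ignores them, so the 48-hour contrast may be confounded in a direction the documents cannot settle

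*Combined protocol and SAP*

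**What the plan says.** Section 2.1 sets up four cohorts: 1) "not on either a chronic β -blocker or ACE-Inhibitor, 2) on chronic β -blocker, 3) on chronic ACE-Inhibitor, and 4) on both". Section 4.1 repeats the rule when patients are identified: "Patients will be stratified into 4 groups: 1) not on either a chronic β -blocker or ACE-Inhibitor". The exclusions in 3.2 and 4.1 do not mention other antihypertensives.

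Section 13.1 describes the reference group differently: "estimated 48h cumulative mean dose for norepinephrine patients not on anti-hypertensives will be 50 mg (SD = 10". The three exposed cohorts are given a common lower mean: "for beta blocker, ACE-Inhibitor, and beta-blocker + ACE-Inhibitor groups will be 25 mg (SD = 10".

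The plan treats the other drugs as of interest. A secondary objective in 1.2 reads "To determine cumulative vasopressor dose of patients on chronic calcium channel blocker or other antihypertensives (clonidine, hydralazine, angiotensin-receptor-blocker (ARB". Section 5.1 collects home use of "beta-blockers, ACE-inhibitors, amlodipine, diltiazem, ARBs, hydralazine, clonidine", and also of hctz and loop diuretics. Section 13.2 analyses the 48-hour cumulative dose by ANOVA across the four cohorts, with no covariate, restriction, stratification or sensitivity analysis for these drugs, and it gives no method for the secondary objective on them.

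**The concern.** The plan describes its comparator in two ways: non-users of two drug classes (2.1, 4.1) and patients on no antihypertensive (13.1). Under the first, a patient on an ARB alone counts as unexposed, although an ARB acts on the same renin-angiotensin system as the cohort 3 drug. A patient on a β-blocker and an ARB counts as β-blocker only.

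If the other drugs change vasopressor need and their use differs between cohorts, the unadjusted ANOVA attributes part of their effect to the β-blocker or ACE-inhibitor. The secondary objective has a related weakness. Its patients are spread over four cohorts filled to a quota of 50, so one pooled figure for them would mix in β-blocker and ACE-inhibitor exposure in proportions set by the quota.

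**Working it through.** **Inputs from 13.1.** Means 50, 25, 25 and 25 mg; SD 10; four groups; α = 0.05; planning effect f = 0.25; N = 180 calculated and 200 to be screened in, 50 per cohort.

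**Inputs assumed.** The documents give neither the share of patients on other antihypertensives nor the effect of those drugs. Let p be the share in cohort 1, q the share in each of cohorts 2–4, and g the effect of the other drugs as a fraction of the β-blocker/ACE-inhibitor effect.

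**1. The plan's own figures.** Power is that of the noncentral F with λ = N·f² and N − 4 denominator degrees of freedom.
- The SD of the four means is 25 × √3/4 = 10.825, so f = 10.825/10 = 1.0825. At N = 20 power is 0.961, as the plan's output shows.
- With f = 0.25 and N = 180, λ = 11.25 and power is 0.804, as stated. At N = 200 power is 0.848.

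**2. Size and direction of the distortion.** With additive effects, the cohort 1 mean is 50 − 25gp and each exposed mean is 25 − 25gq. The contrast is therefore 25 × [1 − g(p − q)]. Taking g = 1:

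| p (cohort 1) | q (cohorts 2–4) | Contrast (mg) | 0.25 scaled alike | Power, N = 200 |
|---|---|---|---|---|
| 30% | 0 | 25 × 0.7 = 17.5 | 0.175 | 51.8% |
| 20% | 20% | 25 × 1.0 = 25 | 0.25 | 84.8% |
| 20% | 40% | 25 × 1.2 = 30 | 0.30 | 95.5% |

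If the other drugs add nothing for a patient already on a β-blocker or ACE-inhibitor, the exposed means stay at 25 mg. The result is then the q = 0 row even when use is equal across cohorts. If g = 0 nothing changes. If the other drugs raise vasopressor need (g < 0), the directions reverse.

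**3. Worst case for dilution.** Here q = 0 and g = 1, f is multiplied by (1 − p), and the within-group SD is held fixed:

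| p | f | Power, N = 180 | Power, N = 200 |
|---|---|---|---|
| 0 | 0.25 | 80.4% | 84.8% |
| 15% | 0.2125 | 65.1% | 70.3% |
| 30% | 0.175 | 47.2% | 51.8% |
| 40% | 0.15 | 35.5% | 39.3% |

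**4. The same worst case on the 50 versus 25 mg scenario.** At p = 40% the contrast is 25 × 0.6 = 15 mg. The cohort 1 variance becomes 100 + 625 × 0.4 × 0.6 = 250, and the pooled SD is √[(250 + 3 × 100)/4] = 11.73. Then f = 15 × 0.433/11.73 = 0.55, and power exceeds 99.9% at N = 180 and at N = 200. Loss of power is thus an issue only on the scale of f = 0.25.

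**5. Restricting cohort 1 alone.** Take 30% use in every cohort, with g = 1 and additive effects. As written, the means are 50 − 7.5 = 42.5 and 25 − 7.5 = 17.5, a contrast of 25 mg. With users removed from cohort 1 only, it is 50 − 17.5 = 32.5 mg, which is 30% too large. With users removed from all four cohorts it is 50 − 25 = 25 mg.

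**The case against.** A reader might infer that the cohort definition dilutes the primary contrast. The documents do not support that. Dilution requires the other drugs to lower vasopressor dose and also to be commoner in cohort 1 than in cohorts 2–4, or to act less than additively. Section 2.2 says that little is known about these effects, and nothing in the plan gives the shares.

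A reader might also infer that the study is underpowered because its reference mean comes from a narrower population. That does not follow either. Section 13.1 says the effect in septic shock is unknown and sets N from a generic f = 0.25, which is not tied to any definition of the reference group. The 50 mg figure feeds only the preliminary calculation.

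It can also be argued that non-users of the two study classes are a coherent comparator for the objective in 1.2, which concerns β-blockers and ACE-inhibitors and does not promise a comparison with untreated patients. That stands, and it is why redefining cohort 1 is not recommended: step 5 shows that doing so can create bias. The description in 13.1 may be no more than shorthand taken from the cited study, which cannot be checked from the documents. Finally, the secondary objective is descriptive and can be met from the fields in 5.1, so it is not uninterpretable; it only needs to be reported by cohort.

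What remains is that the plan describes its comparator in two ways, and that the primary analysis ignores recorded drugs which the plan itself considers relevant.

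**Conclusion.** The point holds as possible confounding of unknown direction and size. Users of other antihypertensives can be in any of the four cohorts, 13.1 describes a narrower reference than 2.1 and 4.1 define, and 13.2 does nothing about it. Under the assumed shares with equal, additive effects, the plan's 25 mg contrast could read anywhere from 17.5 to 30 mg, or be unaffected. The fall in power to 65%, 47% and 36% at N = 180 (70%, 52% and 39% at N = 200) is a worst-case illustration: it puts other drugs in cohort 1 alone, gives them the full effect, and scales a generic f. It is not a forecast. The remedy is cheap and worth making before the data are analysed, because a comparator chosen afterwards becomes an analyst's option.

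**What to change.** 1. Keep the four cohorts as the primary grouping. Use one description of the reference in 2.1, 4.1 and 13.1, and say that cohort 1 may include users of other antihypertensives.
2. Add to 13.2 a pre-specified sensitivity analysis that repeats the 48-hour comparison after removing, from all four cohorts alike, patients on any other antihypertensive recorded under 5.1. State whether hctz and loop diuretics count. Add a second repeat that removes ARB users only. Alternatively, adjust for these drugs as covariates in the primary model.
3. Tabulate use of each drug by cohort, and report the secondary objective on other antihypertensives by cohort and not as one pooled figure.

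Cost: protocol wording and a few extra analyses; 5.1 already collects every field. The restricted analysis is smaller. If 30% of each cohort were removed (an assumption), 35 per cohort would remain, standard errors would rise by a factor of 1/√0.7 = 1.20, and omnibus power at f = 0.25 would be about 68% (N = 140). The restricted reference group will also have less hypertension, so the result should be read beside the comorbidity table as a check on the primary analysis and not as its replacement.
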